A Triple Blinded Randomized Controlled Trial of Oral Melatonin in Elevated
Blood Pressure Individual

NCT number: IR.TUMS.MEDICINE.REC.1397.438

Approval date: 2018-9-17

Document date: December first 2018

Introduction:

Prescription of exogenous melatonin has been proved to decrease nocturnal hypertension, the pulsatility index of internal carotid artery, platelet aggregation, and catecholamine levels (1). Melatonin effects are both receptor mediated and receptor independent. Receptor-mediated effects of melatonin comprise of membrane melatonergic receptors (MT1 and MT2) located in vascular system and heart. And also could be found in cardiomyocytes, left ventricle, and coronary arteries (2, 3).

Antioxidant and mitochondrial-protecting effects are receptor independent effects of melatonin (4). Melatonin levels decreased in pathological conditions including hypertension with no dipper pattern, (5) congestive heart failure (CHF) (6) Ischemic heart disease (4) acute myocardial infarction (7), coronary artery disease (CAD) (1) and low level of LDL-c (8). Melatonin attenuates blood pressure (BP), vascular reactivity, and circulating catecholamine versus placebo in healthy individuals (9-11). Besides, antioxidant effect, anti-inflammatory properties, and metabolic regulator activity of melatonin are also play an important role in introduction of melatonin as a potential therapeutic agent in hypertension and cardiovascular disease (CVD). Accordingly, Clinical trials have been conducted to evaluate antihypertensive effects of melatonin in different settings including:

A double-blind, placebo-controlled study in 2004 demonstrated that oral daily melatonin therapy with 2.5 Mg for 3 weeks significantly decreased systolic and diastolic BP in 16 male hypertensive patients (12). In a crossover randomized double blinded placebo controlled trial in 2005 eighteen women with normal BP or treated essential hypertension allocated to a 3-week course of slow-release 3Mg melatonin pill or placebo one hour before bedtime. They concluded that melatonin may improve the day-night rhythm of BP, particularly in women with a blunted nocturnal BP decline (13).

Effectiveness and safety of melatonin on nocturnal hypertension was investigated in an RCT in 2006. Thirty eight treated hypertensive patients underwent four weeks controlled release melatonin 2 mg or placebo two hours before bedtime. Bottom line was significant anti- hypertensive effects of controlled-release melatonin. Whereas fast-release did not control nocturnal hypertension (14)

In a placebo controlled trial effects of 1.5 Mg melatonin for two weeks in 97 hypertensive and normotensive individuals have been investigated in 2015 results have been shown that both systolic and diastolic BP was significantly mitigated (15).

In an RCT among 44 women in 2015 bedtime prescription of 6 Mg melatonin significantly decreased mean serum level of; Hs-CRP, TNF-alpha and IL-6 versus placebo (16).

Decreased level of plasma norepinephrine and blood pressure (BP) were found in an RCT study in 14 men after 90 minutes of prescribing 2 Mg melatonin versus placebo (17).

In a clinical trial in twenty healthy volunteers in 2014 to evaluate the safety and tolerability of 20, 30, 50, and 100 Mg oral doses of melatonin. Apart from transient drowsiness no adverse effects have been reported. Sleeping pattern has not been changed with melatonin prescription (18).

Therefore, melatonin is appealing in medical practice both in primary and secondary prevention arena because of lack of side effect and availability of this medication.

In a cross over double blinded trial 5Mg melatonin versus placebo was given to 47 mild to moderate hypertensive outpatients associated with Nifedipine 30 or 60 Mg a day. Results have been shown that

melatonin can impair antihypertensive effect of calcium channel blockers, suggesting caution in concomitant use of melatonin and antihypertensive agents (19).

A clinical trial in 60 coronary artery disease (CAD) patients and non-dippers has been conducted to evaluate efficacy of 5 Mg melatonin versus placebo along with previous treatment of CAD. After, completing 90 days of follow up they concluded that prescription of melatonin in patients with high normal value of BP is not recommended because of the nocturnal decrease and daytime increase in BP observed in melatonin intervention group (20).

An RCT in 63 patients with metabolic syndrome has been conducted to evaluate the efficacy of 5 Mg melatonin for two months. Results revealed that BP and lipid profile significantly decreased and anti-oxidative defence significantly improved after two months of melatonin therapy (21).

In a small sample size clinical trial in 12 young women cardiovascular effects of one Mg melatonin versus placebo has been assessed along with a fixed dose of monophasic contraceptive pill. Melatonin significantly reduced systolic and diastolic BP and pulsatility index of internal carotid artery (22).

Therefore, large scale clinical trials are needed to evaluate the efficacy of melatonin on decreasing systolic and diastolic blood pressure. Aforementioned evidences have been shown the safety and efficacy of melatonin prescription in different clinical settings. Moreover, prescription of melatonin in hypertensive patients (20) and associated with other antihypertensive medications (19) have not been recommended. Therefore, we are going to evaluate the efficacy of melatonin versus placebo in pre-hypertensive individuals who have been recognized as at higher risk of developing future hypertension.

BP consists of systolic (the upper number) BP which indicates how much pressure the blood is exerting against artery walls when heart beats. And diastolic BP (the lower number) is indicative of the amount of pressure that blood is exerting against artery walls when the heart is resting between beats. Diagnosis and treatment of hypertension (HTN) depend on accurate measurement of blood pressure and also an average level of BP over a long duration. The last Classification of BP is: Normal blood pressure(systolic blood pressure(SBP) < 120 mmHg or diastolic blood pressure(DBP) < 80 mmHg), elevated blood pressure(SBP=120-129 mmHg or DBP < 80 mmHg), hypertension (stage 1; SBP=130-139 mmHg or DBP=80-89 mmHg), (stage 2; SBP >= 140 mmHg or DBP >= 90 mmHg) (23).

Elevated BP defined as SBP=120-129 mmHg or DBP < 80 mmHg, is associated with higher incidence of hypertension (HTN), cardiovascular events and other end-organ damages such as renal, cerebrovascular and ocular (24,25). It has been shown that life style intervention in elevated BP people can prevent incidence of hypertension. Elevated BP individuals who will not reach optimal BP after receiving lifestyle modification are candidate for more aggressive anti-hypertensive treatment strategies. So, lowering blood pressure in elevated BP people will provide an excellent opportunity to prevent the incidence of HTN. Therefore, we are planning to use a safe treatment option of melatonin associated with life style intervention according to ACC/AHA 2013 guideline (26) in elevated BP individuals to mitigate systolic and diastolic BP to prevent the incidence of HTN.

Ongoing researches:

IMPACT ongoing trial designed in 2014 to test intracoronary versus systemic melatonin in an RCT among patients with acute myocardial infarction (AMI) undergoing primary percutaneous cardiac intervention (27).

Objectives:

Main objective: To determine the efficacy of melatonin in attenuating blood pressure among elevated BP individuals

Specific objectives:

To determine the efficacy of melatonin in attenuation of Systolic and diastolic BP

To determine the effect of melatonin on Hs- CRP level, LDL-c, total cholesterol level and fasting blood sugar (FBS)

To determine the effect of melatonin on sleeping pattern, drowsiness

Hypothesis

Melatonin therapy can lower the systolic and diastolic BP of elevated BP individuals

Melatonin can attenuate levels of circulatory biomarkers such as Hs- CRP

Melatonin can decline the level of total Cholesterol, LDL-c and FBS

Materials, subjects and methods:

Study design: Triple blinded randomized controlled trial (RCT)

Study population: Elevated BP individuals who have systolic blood pressure of 120-129 mmHg or diastolic blood pressure of 80 mmHg

Study sample: Patients admitted in Tehran Heart Centre (THC)

Sampling method: Eligible patients will be recruited with simple random sampling

Inclusion criteria:

-Individuals with blood pressure 120-129 / 80 mmHg

- Age range of 30-60

-Negative pregnancy test for women at productive age

-Baseline melatonin and biomarkers level and complete liver function tests within normal range

Exclusion criteria:

-Previous history of hypersensitivity of melatonin

- Past history of using antihypertensive treatment

- Past medical history of hypertension, cardiovascular diseases and diabetes mellitus, epilepsy and other physician documented diseases

- Use of beta-blockers, sleep aids, warfarin, flaxseed, soy and supplements

-Non- compliance

Sample size:

Sample size calculation is based on the following equation and efficacy of melatonin in reducing systolic and diastolic blood pressure published in an RCT in 2004 by Scheer F et.al:

$$N = \frac{(1/f) (z\alpha + z\beta)^2 (s1^2 + s2^2)^2}{(X1 - X2)^2}$$

N=160 per arm

N_{total}= 320

Informed consent:

Written consent form according to Helsinki Declaration will provide participants with information about intervention including: benefits and harms, cost, methods of measuring out comes, follow up intervals, physician visits, and study team. Participants who accept to randomly assign to the trial arms are going to allocate to treatment versus placebo arm.

Study design: Randomized controlled trial (RCT), parallel two arms study

Intervention plan:

Recruitment: 320 cases of elevated BP will recruit to the study based on eligibility criteria with a simple random sampling method during screening visits by the physicians from THC.

Treatment plan: Three weeks melatonin 3Mg or placebo one hour before bedtime has been planned. All of the melatonin and placebo capsules will be supplied from a single hospital pharmacy and free of charge to the participants. Melatonin and placebo capsules will be identical. Participants will receive a three weeks supply at the assignment time. Besides, all participants will receive a careful plan of adherence to a heart-healthy diet, regular exercise, avoidance of tobacco use and maintenance of a healthy body mass index (BMI) according to 2013ACC/ AHA guideline (the last version).

Comprehensive written intervention protocol will be circulating at treatment assignment time.

Treatment arms: Melatonin 3 mg versus placebo

Treatment allocation: After completing informed consent and prior to randomization, all participants undergo complete physical examination and laboratory test. Baseline melatonin level, inflammatory biomarkers and pregnancy test (for women in reproductive age) will be performed. Sleep quality, actual sleep time, and sleep latency will be recorded.

320 participants will be assigned to melatonin 3 mg versus placebo arm using balanced randomization.

Randomization scheme: Balanced randomization using computerized random digit table will be used.

Blinding: Triple blinding is planned. All participants, medical providers and outcome evaluators will be blinded about treatment arms.

Measurements:

Two ambulatory blood pressure (BP) recording have been planned while using melatonin versus placebo during three weeks intervention period. First measurement will be at recruitment time and the second one at the end of three weeks intervention.

We have also planned to measure melatonin level at baseline, inflammatory biomarkers, liver function tests, lipid profile and sleep details.

Follow up:

Duration: Three weeks

Active follow up:

Written intervention protocol will be circulating at treatment assignment time. Weekly telephone contact with participants will assess adherence to the protocol and will obtain weekly counts of the melatonin or placebo capsules, recall for ambulatory BP measurement at the end of three weeks.

Out comes:

We will assess lowering blood pressure, sleep details using Pittsburgh sleep quality questionnaire (PSQI), inflammatory biomarkers, liver function test and adherence to ACC/AHA 2013 guideline regarding heart-healthy diet (step one national cholesterol education program), regular exercise (moderate level exercise 30 minutes a day five times a week), avoidance of tobacco use and maintenance of a healthy body mass index (BMI= 21-25) at baseline and after completion of the 3 weeks follow up period. All clinical evaluations including efficacy of the treatments, side effects will be assessed by a different blinded clinician. Costs of a trial will be calculated by the research team.

All blood samples will be fasting sample which will be processed, stored and assessed by one hospital laboratory.

Laboratory methods: Standardized lab method using international or local kits will be used.

Data collection: standardized questionnaire will be used to record the results of complete physical examination by physicians, anthropometric measurement, blood pressure measurement, ECG, and biological measurement such as inflammatory biomarkers and electrolytes and outcome variables such as BP, BMI, physical activity, ECG findings. Sleep quality and details of sleep will be detected with standard questionnaire.

Data management plan:

Data coding, entry, cleaning, and analysis will be performed by data analyser team.

Data analysis protocol:

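### The sample-size equation squares the variance sum, so its answer depends on the unit of pressure; with no inputs stated, 160 per arm can be neither reproduced nor refuted.

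*Combined protocol and SAP*

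**What the plan says.** In the combined protocol and SAP, the Sample size section rests the number on two things. One is an equation: a factor 1/f, times "z\alpha + z\beta)^2", times a variance term over a squared difference, printed as "s1^2 + s2^2)^2}{(X1 - X2)^2". The other is the "efficacy of melatonin in reducing systolic and diastolic blood pressure published in an RCT in 2004". The result is 160 per arm and 320 in total. Under Treatment allocation, "320 participants will be assigned to melatonin 3 mg versus placebo arm using balanced randomization".

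No value is given for alpha, the side of the test, power, s1, s2, X1, X2 or f, and f is not defined. The section does not say whether systolic or diastolic pressure set the size. The Introduction describes the 2004 study only by its dose, duration and finding that treatment "significantly decreased systolic and diastolic BP in 16 male hypertensive patients", with no effect in mmHg and no SD. The analysis plan adds neither alpha nor power.

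**The concern.** The per-arm size for comparing two independent means has the sum of the two variances to the first power. Here that sum is squared again. The numerator is then in mmHg⁴ and the denominator in mmHg², so the result is in mmHg² and is not a count of people. This equation is the only calculation shown for 320 participants.

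At stake is the link between the trial's size and a stated target. Without a correct equation and its inputs, a reader cannot say which difference the trial was designed to detect, and so cannot judge whether a null result is informative.

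**Working it through.** **Reproducing 160.** This cannot be done from the documents, because no input is stated. All inputs below are assumptions: equal SDs (s), f = 1, two-sided 5% and 80% power unless noted, so (1.960 + 0.842)² = 7.849.

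**Formulas, per arm, with difference d**
- Printed: N = 7.849 × (2s²)² / d²
- Conventional: N = 7.849 × 2s² / d²
- Ratio of the two: 2s², which itself depends on the unit.

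**Unit check, s = 10 mmHg, d = 5 mmHg**
- Printed, in mmHg: 7.849 × 200² / 25 = 12,558
- Printed, same data in cmHg (s = 1, d = 0.5): 7.849 × 2² / 0.25 = 125.6, or 126
- Conventional, in mmHg: 7.849 × 200 / 25 = 62.8, or 63; in cmHg: 7.849 × 2 / 0.25 = 62.8, again 63

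**Difference at which each form returns 160**

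| Assumed SD (mmHg) | Printed: 2s² × √(7.849/160) | Conventional: √(7.849 × 2s²/160) |
|---|---|---|
| 8 | 28.4 | 2.51 |
| 10 | 44.3 | 3.13 |
| 12 | 63.8 | 3.76 |

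**Small SDs.** At s = 3, d = 4 the printed form gives 7.849 × 18² / 16 = 158.9, close to 160. The conventional formula there gives 7.849 × 18 / 16 = 8.8, or 9 per arm. For differences of 2 to 10 mmHg the printed form returns 160 at SDs of 2.1 to 4.75 mmHg.

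**What 160 evaluable per arm delivers, conventional formula, two-sided 5%**
- 80% power: 2.802 × √(2/160) = 0.313 SD (exact t-test 0.314)
- 90% power: (1.960 + 1.282) × √(2/160) = 0.362 SD (exact t-test 0.364)

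**With attrition.** If f were a retention fraction of 0.8 (an assumption), 160 × 0.8 = 128 per arm would be evaluable. Since √(2/128) = 0.125, the detectable differences are 2.802 × 0.125 = 0.35 SD at 80% power and 3.242 × 0.125 = 0.41 SD at 90%.

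**The case against.** Four points can be made for the plan.

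First, a reader might infer that the printed equation cannot give 160 at any plausible blood-pressure spread. The documents do not support that. They state no SD, and the equation does return about 160 at SD 3 and difference 4. The entry criterion, "Individuals with blood pressure 120-129 / 80 mmHg", points to a small systolic spread at screening: a uniform distribution over 9 to 10 mmHg has SD 9/√12 = 2.6 to 10/√12 = 2.9. This stands. However, the window governs entry, whereas the outcome is ambulatory pressure: "First measurement will be at recruitment time and the second one at the end of three weeks intervention". The SD of that outcome is not given and may be larger. A match at a small SD would not validate the equation either, since about 9 per arm would then suffice.

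Second, nothing shows that 160 was computed with the printed exponent. It may be a typing slip, or an error in reading the formula from the PDF. This stands too, and is why the source page should be checked. It leaves the missing inputs untouched.

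Third, the 2004 trial is part of the stated basis, and its figures are not in the documents. Whether they support 160 cannot be decided here.

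Fourth, stating what 320 delivers could put a back-calculated justification in place of the planned one. That is a fair warning. The source inputs should be run first, and the detectable difference labelled as a description of the fixed enrolment.

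**Conclusion.** The equation as printed is dimensionally wrong, and with no inputs stated the figure of 160 per arm is unverified. For assumed SDs of 8 to 12 mmHg (two-sided 5%, 80% power, f = 1) it returns 160 only for differences of 28 to 64 mmHg. At SDs small enough for it to return 160 with a modest difference, it overstates the need many times over.

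It would be tempting to conclude that 320 is the wrong number, or that its stated basis fails to support it. Neither follows, because 160 fits the conventional formula at unremarkable values such as SD 10 and a difference of 3.13 mmHg.

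A reader might also infer a loss of power from a one-sided z. If z-alpha had been 1.645, a nominal 80% or 90% design would have about 70% or 83% power at two-sided 5%. No such value appears in the plan, so this is hypothetical and only shows why the side must be stated.

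Type I error, estimates and confidence intervals are unaffected. What is wrong is the written derivation of the trial's size.

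**What to change.** 1. Check the exponent against the source page. If it is there, replace (s1² + s2²)² by (s1² + s2²).
2. Recompute with the inputs actually used and print them: the blood-pressure measure, both SDs, the target difference, two-sided alpha, power, the meaning and value of f, and any dropout allowance.
3. Keep 320 and add a sentence such as: at two-sided 5%, 160 evaluable participants per arm give 80% power for a between-arm difference of 0.31 SD and 90% for 0.36 SD. Give the corresponding figures for the evaluable number expected after dropout; at an assumed 128 per arm they are 0.35 and 0.41 SD.
4. If the inputs do not return 160, restate the detectable difference or the power, not the enrolment.

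The cost is one equation and a few sentences, with no added participants. The stated power or detectable difference may turn out less favourable than the sponsor assumed.
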